12.2 Brief Behavioral Compliance Enhancement Treatment (BBCET)

The BBCET is a brief (15 to 30 minutes per session) standardized treatment program to be used in conjunction with a pharmacological intervention for the treatment of alcohol dependence.[57] The purpose of the treatment is to increase and enhance compliance with the investigational products and other aspects of the treatment regimen. Each session addresses subject issues

related to the personal barriers of compliance, focuses on how medication can assist the subject in achieving goals related to the control of drinking and smoking, and, if necessary, addresses management of side effects. The treatment emphasizes the role of medication and setting drinking and smoking goals. Sessions will be audiotaped and 10% of tapes will be centrally reviewed by staff at University of Virginia Health System. Subjects may decline to have their sessions audiotaped.

Research staff involved in counseling the subjects will be trained to deliver BBCET and will have to pass a certification procedure ratified by [name] (Overall PI) or a designee. Training will include didactic meetings with the therapy supervisor, reading assignments, and review of at least one training case. [name] or a designee also will also conduct any additional training sessions, as needed. To monitor and prevent practitioner deviation from the protocol, about 10% of the recorded sessions will be selected at random for evaluation of quality and adherence to manual guidelines. Monthly conference calls to discuss issues with the BBCET will be used as another measure to monitor protocol adherence and to take necessary steps to correct any deviation from the allowed procedure. Supervision of practitioners at all sites will be coordinated through [name] or a designee at the University of Virginia (UVa). Practitioners will remain blind to the subjects' medication condition.

A subject checklist and survey form will be designed to measure the type and amount of treatment received. This checklist, administered at the end of every session, also will serve as an index of treatment acceptability and perceived helpfulness.

Subjects who cannot tolerate the medication or who need to reduce or stop the medication for other reasons will still be allowed to take part in the BBCET and other aspects of the study.

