13.5 One and three month follow-up visits

At the end of the treatment period, subjects will be scheduled to attend a follow-up assessment session at one month post-treatment and take part in a follow-up phone call at three months post-treatment.

The following assessments will be administered at the one month follow-up visit: Fagerström Test for Nicotine Dependence, Q-LES-Q, The Alcohol Craving Visual Analog Scales, The Nicotine Craving Visual Analog Scales, CIWA-AR, Wisconsin Smoking Withdrawal Scale, PANAS, and CES-D. In addition, TLFBS for smoking and alcohol consumption and BAC and CO level will be collected at this visit. During the 3 month follow-up phone call, the CIWA-AR will be administered and TLFBS for smoking and alcohol use will be performed.

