13.6 Early Termination (ET)

If a subject wishes to withdraw from the study before completing all study visits during the treatment phase then the study staff will schedule an early termination visit. The early termination visit will include all procedures and assessments of visit number 15 (week 19).

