The decision to break the study blind for an individual subject lies with the study principal investigator (or a designated co-investigator if a PI is not available) at each site and [name] [name]. Breaking the study blind will be resorted to only in cases of a life-threatening emergency when knowledge of the treatment arm investigational agent will influence clinical management. A designated study staff member will contact [name] [name] ([contact], [contact], [name]) in the event that the site PI believes the blind needs to be broken. Once permission has been granted by [name], a designated staff member at UVa will match up the pill bottle number for the subject with the master list of dose conditions to disclose which medication the subject was assigned.

g) Subject withdrawal

An investigator may terminate a subject if he or she deems it clinically appropriate or for any of the following reasons: 1) significant side effects from the medication, 2) serious or unexpected adverse events, 3) inability to comply with the study protocol, 4) protocol violation, or 5) serious inter-current illness. A subject may withdraw from the study anytime he or she wishes. In the

event that a subject is discontinued from receiving the research medication, he or she will be allowed to continue the psychosocial interventions with the approval of the investigator.

Any subject who discontinues prematurely, regardless of the reason, will be requested to return for a final visit to perform the necessary procedures and obtain data for the end-of-study/early-termination visit.

h) Adverse event reporting

In accordance with FDA reporting requirements, all adverse events (AEs) occurring during the course of the clinical trial will be collected, documented, and reported by the investigator or sub-investigators at each site. Policies established by the local IRB at each site will be followed with regard to reporting AEs.

An adverse event is any untoward, unfavorable or unintended sign (including an abnormal laboratory finding), symptom, or disease, temporally associated with the use of the product under investigation, whether or not related to the product under investigation.

An unexpected adverse event is any adverse drug experience, the nature, specificity, or severity of which is not consistent with the investigator's brochure, package insert or the general investigational plan.

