15.4 Subject Populations

The ITT population will be used for the primary analysis and is defined as the subjects who are randomized into the study. The evaluable population is defined as those subjects randomized to the study who completed at least 6 consecutive weeks of maintenance investigational product administration with a dose of at least 50 mg per day for at least 5 days of each 7-day weekly period. The safety population includes all subjects who received at least one dose of investigational product.

Analysis: Data will be summarized with respect to the primary and secondary outcome measures, demographics, and baseline characteristics. In general, quantitative variables will be summarized with standard descriptive statistics (e.g., range, quartiles, means, standard deviations), while frequency tables will summarize categorical variables. Group comparison for quantitative variables will be performed using standard two-sample t-tests or analysis of variance as appropriate. Highly skewed variables may be transformed prior to inferential comparison, or non-parametric methods may be used if needed. Group comparison for categorical variables will be analyzed with two-sample comparisons of proportions, or chi-square tests as appropriate.

The primary efficacy variables will be the PHDD for the drinking outcome and the continuous abstinence rate for the smoking outcome (during the last 4 weeks of treatment, i.e., weeks 15–18 inclusive), respectively. The secondary efficacy variables will be quality of life and measures of alcohol and nicotine craving.

Exploratory outcome variables will include other: 1) measures of drinking severity (i.e., DDD) and abstinence (i.e., percentage of days abstinent; PDA) averaged across either the entire double-blind period or the last 4 weeks of treatment, and 2) smoking measures including the point prevalence abstinence rate and the CO level over either the entire double-blind period or the last 4 weeks of treatment; 3) psychological assessments including measures of nicotine and alcohol withdrawal (WSWS, MOS-Sleep, CIWA-Ar), negative affect (PANAS, CES-D), dependence (FTND), drinking behavior (DrInC) and compliance (BBCET).

The general approach to statistical analyses will be the same as what we utilized in our previous studies.[4, 5] All randomized subjects will be included in the analysis using the intent-to-treat principle. Statistical analyses will be conducted using SAS 9.1 (SAS Institute Inc., Cary, NC).[6]

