15.5 Sample Size Calculation

We did two sets of power analysis to account for the drinking and smoking endpoints in our proposed study. Importantly, because smoking outcomes are based mostly on dichotomous variables, power estimates for these outcomes drive the numbers needed for this comorbid alcohol- and nicotine-dependent cohort. Hence, it is important to have adequate power for the smoking outcomes even though this will result in a superfluous level of power for the drinking outcomes.

First, for the smoking outcomes, we did a power analysis by comparing the two-sample difference in nicotine abstinence using SAS Proc POWER. We have estimated power based upon our ability to detect a difference in the percentage of smoking abstinence between the treatment groups. Because the comparisons of the topiramate groups with one another (i.e., high vs. low) and with placebo are experimental, we chose to calculate power to detect the effect size of therapeutic treatments typical of the smoking cessation literature. We chose to calculate power based on our estimates of the percentage of smoking abstinence in the pivotal study by Jorenby et al.,[72] where bupropion was compared with placebo in a 9-week randomized, controlled clinical trial. In that study, the TQD occurred at the end of the first week of double-blind treatment. As a conservative measure, we have accepted the subject numbers for these two groups for the present study to represent the comparison of the low-dose topiramate vs. placebo or the high-dose vs. low-dose topiramate. Thus, we have assumed that the difference between low-dose topiramate and placebo would be similar to that between high- and low-dose topiramate. Since there are 3 pairwise comparisons between the three arms, we will adopt Bonferroni's adjustment and take alpha level as $0.05/3 = 0.017$.

From Figure 1 in Jorenby et al.,[72] the continuous prevalence rate of smoking abstinence at 18 weeks is approximately 10% for placebo and 28% for bupropion. Using these numbers, we find that 98 subjects in each arm (294 in total) are needed to achieve a power of 0.80. If we observe a similar effect to that in the preliminary study we will be operating under even increased power.

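### Sections 12.2, 13.6 and 13.10 g) disagree on follow-up after early stopping, and nothing requires drinking and smoking data for weeks 15–18 from a participant who leaves before then

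*Combined protocol and SAP*

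**What the plan says.** - **Section 12.2** covers participants who cannot tolerate the medication, or who reduce or stop it. They "will still be allowed to take part in the BBCET and other aspects of the study". No approval is needed. Section 13.12 adds that payment for attended visits does not depend on still taking the product.
- **Section 13.10 g)** says of a participant taken off the medication that "he or she will be allowed to continue the psychosocial interventions with the approval of the investigator". It does not mention outcome assessments. It continues: "Any subject who discontinues prematurely, regardless of the reason, will be requested to return for a final visit". The purpose of that visit is to obtain the end-of-study or early-termination data.
- **Section 13.6** has a different trigger. If a participant wants to leave the study during the treatment phase, "then the study staff will schedule an early termination visit", using the procedures of visit 15.
- **Section 13.5** sets a visit one month after treatment and a call at three months: "During the 3 month follow-up phone call, the CIWA-AR will be administered and TLFBS for smoking and alcohol use will be performed". It does not say whether early stoppers receive these contacts.
- **Sections 15.1 and 15.4** place both primary outcomes, percentage of heavy drinking days (PHDD) and continuous smoking abstinence, in weeks 15–18. Section 15.4 adds: "All randomized subjects will be included in the analysis using the intent-to-treat principle". It fixes no rule for missing outcomes and says only that other methods will be considered if attrition is informative.
- **The abstract** expects 30% dropout, with 206 of 294 completing 18 weeks.

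**The concern.** The sections can send the same participant down two paths. Under 12.2, someone who stops the drug at week 7 can go on being assessed. Under 13.10 g) read with 13.6, the same person may have one closing visit at week 7, after which no section requires anyone to ask about weeks 15–18.

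An intention-to-treat analysis of weeks 15–18 needs an outcome from that window for every randomized participant. A later model can make assumptions about days that were never recorded, but it cannot restore them. Side effects are a listed reason for termination in 13.10 g), so the loss may be related to treatment arm. It may also vary by site, according to which section the staff follow.

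**Working it through.** **1. The sections side by side.** Sections 12.2 and 13.12 deal with stopping the drug and foresee further visits. Section 13.6 deals with leaving the study. Section 13.10 g) speaks of discontinuing for any reason without saying which of the two it means. None of them requires TLFB for weeks 15–18 after the closing visit.

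**2. Calendar.** Week 15 starts on day 14 × 7 + 1 = 99, and week 18 ends on day 18 × 7 = 126.
- If the follow-up contacts are counted from day 126, they fall at about day 126 + 30 = 156 and day 126 + 90 = 216. The first looks back 156 − 99 = 57 days to the start of the window. The second looks back 216 − 126 = 90 to 216 − 99 = 117 days.
- If they are counted from the participant's own last dose, stopping at the end of week 5 (day 35) puts them at about days 65 and 125, both before the window closes. Stopping at the end of week 7 (day 49) puts them at about days 79 and 139, and only the second falls after the window.
- A contact in week 19 (days 127–133) looks back 28 to 34 days to day 99. That is well inside the three-month recall that section 14.18 uses at baseline.

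**3. Number affected.** 294 × 0.70 = 205.8, which is the stated 206. Then 294 − 206 = 88.

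**4. The plan's own sample size.** Section 15.5 uses abstinence of "approximately 10% for placebo and 28% for bupropion", alpha 0.017 and power 0.80. With mean rate p̄ = 0.19:

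n = [z(α/2)·√(2p̄(1−p̄)) + z(β)·√(p1(1−p1) + p2(1−p2))]² / (p2−p1)²

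= (2.387 × 0.5548 + 0.842 × 0.540)² / 0.18² ≈ 97.7, so 98 per arm. This matches the plan for a two-sided test and contains no dropout allowance. Keeping 98 observed per arm at 30% dropout would take 98/0.70 = 140. Section 15.5 says no allowance is needed, but its reason rests on the mixed model behind the drinking calculation. The 76 per arm for drinking cannot be reproduced, because the size of the earlier trial is not given.

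**5. Smoking power if the window is lost** (alpha 0.05/3, two-sided, z = 2.394). This assumes equal dropout across arms, no weeks 15–18 data from any dropout, and the planning rates in everyone.

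Power = Φ{[√n·(p2−p1) − z·√(2p̄(1−p̄))] / √(p1(1−p1) + p2(1−p2))}

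- Complete cases, n = 98 × 0.70 = 68.6: (8.283 × 0.18 − 2.394 × 0.5548)/0.540 = 0.30, so power is 0.62.
- Missing counted as smoking, rates 0.7 × 10% = 7% and 0.7 × 28% = 19.6%, n = 98: (9.899 × 0.126 − 2.394 × 0.4802)/0.4719 = 0.21, so power is 0.58.

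| Share of dropouts recovered | Observed per arm | Complete-case | Missing = smoking |
|---|---|---|---|
| None | 68.6 | 0.62 | 0.58 |
| Half | 83.3 | 0.72 | 0.70 |
| All | 98 | 0.80 | 0.80 |

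With no recovery, complete-case power is 0.69 at 20% dropout and 0.54 at 40%. The rows with recovery assume that reported abstinence from these participants is accepted.

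**6. Drinking.** Suppose the full arms have equal mean PHDD M, a share d stops, and stoppers exceed stayers by Δ. The observed-case mean is then M − d × Δ, and the difference between arms is (d_high − d_placebo) × Δ. The documents give neither input. Assumed gaps of 10 to 30 percentage points in dropout and 10 to 30 points in PHDD give 0.1 × 10 = 1 up to 0.3 × 30 = 9 points, for example 0.2 × 20 = 4, in favour of the high dose with no true effect.

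**The case against.** The sections can be read together. Paragraph g) is about subject withdrawal and its visit closes the study, so it may apply only to people who leave the study, with 12.2 and 13.12 governing those who merely stop the drug. Paragraph g) does not restrict participants to psychosocial treatment in so many words. Counselling is also delivered at the visits where section 13.4 has TLFB taken, so a participant who keeps attending would be assessed. This stands as a reasonable reading, but it is not the only one. It also leaves the gap for people who do leave the study, since nothing asks for a later outcome contact.

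Section 13.5 does not exclude early stoppers, and its contacts include TLFB. That also stands. Whether they reach weeks 15–18 depends on an unstated starting point, as step 2 shows, and the recall period for those contacts is not given.

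The 88 are people not expected to complete treatment. Some will refuse contact or be lost, and some may leave after part of the window has been recorded. It is an upper bound.

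The bias figures come from assumed inputs and an unadjusted observed-case comparison, whereas section 15.4 plans baseline adjustment. Section 5.2.4 describes the planned doses as well tolerated and links some nervous-system effects to doses above them. Higher dropout on the high dose is therefore plausible, but the documents do not state it.

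**Conclusion.** The sections conflict, and on one legitimate reading no primary-window data are required from early leavers. Up to about 88 of 294 participants could be affected. If all of them lacked the window, smoking power would be about 0.62 or 0.58 instead of 0.80. The loss is smaller if the cited 10% and 28% already count dropouts as smokers, which the documents do not say. The direction and size of any PHDD bias depend on two unknown gaps.

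A reader might infer more than this, without support:
- That weeks 15–18 will be lost for everyone who stops the drug. Section 12.2 permits continued assessment, and no section orders it to end.
- That a telephone TLFB restores both primary outcomes. It gives PHDD and settles admitted smoking. Reported abstinence also needs expired CO below 10 ppm (14.19), which a call cannot supply. Table 1 marks CO at the three-month call, but section 13.5 lists only the withdrawal scale and TLFB. Section 14.26 gives cotinine a half-life of about 19 hours, so one mailed sample reflects recent exposure and not four weeks.
- That early-termination data will be analysed as week 19. Section 13.6 assigns visit 15's procedures to that visit and says nothing about labelling. TLFB is a daily record, so a visit label would not change PHDD.

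**What to change.** Reconcile 12.2, 13.6 and 13.10 g), and define whether discontinuing refers to the drug or the study. Decisions on stopping treatment stay with the investigator; the change concerns data collection only.

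Add one rule:
- Record stopping the drug separately from refusing further contact.
- Every randomized participant who has not refused contact has at least one TLFB contact, in clinic or by phone, at about week 19 counted from randomization and covering weeks 15–18.
- Those who report abstinence are sent the saliva kit already provided for in 13.4 and 14.26. State in advance how reported abstinence without CO readings will be classified.

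The plan already has telephone visits (13.4), telephone TLFB (13.5) and three-month recall (14.18). The cost is protocol wording, at most about 88 extra contacts and some mailed kits. The drawback is recall error over roughly four to five weeks. Keeping every stopper on the full visit calendar is not needed for this purpose.

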13.11 Volunteer Discontinuation

The investigators will follow the protocol to identify and intervene with subjects experiencing clinical deterioration during study participation. Potential protocol discontinuations will be reported to the **overall PI, [name]**.

13.12 Recommended Subject Compensation

Subjects will be compensated for travel expenses and for time contributed to this research study in the form of vouchers, retail scrip, or cash. Compensation amounts will be in accordance with each local site's IRB recommendations. Subjects will be compensated regardless of whether they continue to receive the investigational product, if they attend visits. This compensation is for time and expenses incurred for study participation (e.g., gasoline, public transportation). Compensation for all completed visits, procedures and assessments may be up to \$510.

13.13 Trial Registration

This trial will be registered on the National Library of Medicine's Clinical Trials Registry on the World Wide Web at <http://www.clinicaltrials.gov>.

14 ASSESSMENT METHODS

Table 1 summarizes the timing of the clinical activities and assessments to be conducted over the entire study period. These include the PANAS, Q-LES-Q, The Alcohol Craving Visual Analog Scales, The Nicotine Craving Visual Analog Scales, Wisconsin Smoking Withdrawal Scale, CES-D, MOS-Sleep, DrInC, CIWA-AR, Other Drug Use, and Fagerström Questionnaires.

14.1 AEs

AEs will be assessed starting after the subject takes the first dose of investigational product. AEs assessed in the clinic will use an opened ended question: "How have you been feeling since your last visit?" If an AE is reported that requires medical attention, it should be reported to the medical team for evaluation and follow-up.

14.2 Alcohol Breathalyzer

An alcohol breathalyzer will be administered at consent, at screening, and at every in-clinic visit as a safety measure. Acceptable BAC levels at consent and screening is equal to 0.000 and less than or equal to 0.020 for in-clinic visits.

14.3 Blood Chemistry, Hematology and Urine

Blood chemistry and hematology will be performed to confirm the subjects' physical health. These tests will include: complete blood count (CBC), sodium, potassium, chloride, calcium, phosphorus, total protein, albumin, globulin, glucose, total bilirubin, alkaline phosphatase, albumin/globulin ratio, serum glutamic oxaloacetic transaminase (SGOT), serum glutamic pyruvic transaminase (SGPT), γ -glutamyl transferase (GGT), blood urea nitrogen (BUN), creatinine, uric acid, and lactate dehydrogenase.

Urine will be collected for routine urinalysis. Women of child-bearing potential will receive a urine pregnancy test as scheduled in Table 1. Additionally, women of child-bearing potential participating in this study will be required to use an acceptable form of contraception, which includes but is not limited to the oral contraceptive pill, barrier (diaphragm and condom) plus spermicide, or hormonal or surgical implants.

An onsite urine drug screen will be performed at the screening visit to clear each subject for randomization. This UDS must be negative for all drugs. If a patient tests positive for a drug, he or she will be permitted one repeat urine drug screen prior to randomization. At site PIs' discretion, should a patient test positive again during the repeat UDS, he or she may rescreen (including re-consenting) 30 days from the end of the original 14 day period for randomization, which began when the informed consent was signed at the first screen visit. Urine drug screens will be repeated intermittently throughout the study.

